### **Dose Escalation Part**

The administration of the investigational medicinal product (IMP) will begin at 1 ng/kg, representing the selected safe starting dose for a first-in-human (FIH) trial, based on the Minimal Anticipated Biological Effect Level (MABEL), and by integration of all available in vivo and in vitro data at the start of the study.

A 3+3 dose escalation scheme will be used, based on dose-limiting toxicities (DLTs) observed during the first 42 days following the first administration of the first cycle of treatment. Adverse events (AEs) will be graded according to the National Cancer Institute (NCI) common terminology criteria (CTC) for AEs (NCI-CTCAE) v4.03, except for cytokine release syndrome (CRS), which will be graded according to the 2014 NCI Consensus Guidelines.

In this FIH study, potential DLTs are defined as the following:

- Any Grade ≥3 nonhematological AE, unless either caused by disease
  progression or obviously unrelated cause or caused by a laboratory
  abnormality without associated clinical consequences that resolves within
  5 days (AE's related to cytopenias that were present prior to starting
  SAR440234 or to underlying leukemia will not be considered DLT's).
- Grade 4 hematological toxicities, ie, new onset or worsening of life-threatening hematological abnormalities after administration of SAR440234. (AE's related to cytopenias that were present prior to starting SAR440234 or to underlying leukemia will not be considered DLT's.):
  - Grade 4 bone marrow hypocellularity, if not caused by disease progression and not improved to baseline value or Grade ≤1 within 14 days,
  - Grade 4 decreased neutrophils, if not present at baseline and not resolved to baseline value or Grade ≤1 within 14 days,
  - Grade 4 febrile neutropenia not resolved within 7 days,
  - Grade 4 decreased platelet count, if not present at baseline and not improved to baseline value or Grade ≤1 within 14 days,
  - Grade 4 anemia, if not improved to baseline value or Grade ≤1 within 14 days.
- Grade 3 or Grade 4 CRS.
- Grade 2 CRS if it persists for >48 hours or is present <48 hours before the time when the next planned dose of SAR440234 is due.
- Any treatment-emergent adverse event (TEAE) that, in the opinion of the Principal Investigator and Sponsor, is of potential clinical significance such that further dose escalation would expose patients to unacceptable risk.

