# 6.2.1 Starting dose and dose levels

SAR440234 will be administered IV on Day 1, Day 4 (DL≥3), Day 8, and weekly thereafter in Cycle 1 for a 42-day cycle. The dosing regimen will be weight-based; however, if a patient weighs >140 kg, the patient's weight will be capped at 140 kg for dose calculations. The administration of the investigational medicinal product (IMP) will begin at the selected safe starting dose for an FIH trial, based on the MABEL, and by integration of all available in vivo and in vitro data at the start of the study.

A 3+3 dose escalation scheme will be used, based on DLTs observed during the first 42 days following the first administration of IMP in the first cycle (the DLT observation period). The goal is to treat 3patients per dose level in order to follow a 3+3 design. In this FIH study, potential DLTs are defined as the following:

• Any Grade ≥3 nonhematological AE, unless either caused by disease progression or an obviously unrelated cause or caused by a laboratory abnormality without associated clinical consequences that resolves within 5 days (AE's related to cytopenias that were present prior to starting SAR440234 or to underlying leukemia will not be considered DLT's).

- Grade 4 hematological toxicities as defined in NCI-CTCAE v4.03, ie, new onset or
  worsening of life-threatening hematological abnormalities after administration of
  SAR440234 (AE's related to cytopenias that were present prior to starting SAR440234 or
  to underlying leukemia will not be considered DLT's).
  - Grade 4 bone marrow hypocellularity, if not caused by disease progression and not improved to baseline value or Grade ≤1 within 14 days,
  - Grade 4 decreased neutrophils, if not present at baseline and not resolved to baseline value or Grade ≤1 within 14 days,
  - Grade 4 febrile neutropenia not resolved within 7 days,
  - Grade 4 decreased platelet count, if not present at baseline and not improved to baseline value or Grade ≤1 within 14 days,
  - Grade 4 anemia, if not improved to baseline value or Grade ≤1 within 14 days.
- Grade 3 or Grade 4 CRS.
- Grade 2 CRS if it persists for >48 hours or is present <48 hours before the time when the next planned dose of SAR440234 is due.
- Any treatment-emergent adverse event (TEAE) that, in the opinion of the Principal Investigator and Sponsor, is of potential clinical significance such that further dose escalation would expose patients to unacceptable risk.

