# 6.5.3 Dose delay/modification for cytokine release syndrome and infusion-related reactions

Infusion-related reactions and CRS will be graded according to the 2014 NCI Consensus Guidelines (Appendix H). Recovery is defined as resolution to Grade 1 or less. CRS-like symptoms or signs that occur during infusion will be referred to as infusion-related reactions, while CRS-symptoms or signs that develop or persist after the infusion ends will be referred to as CRS. The patient's temperature, heart rate, blood pressure, oxygen saturation, and respiratory rate will be assessed every 30 minutes during the infusion. If clinical signs of an **infusion-related reaction Grade 1** develop, the infusion will be interrupted, and the patient will be treated with acetaminophen, diphenhydramine, and ranitidine, or similar agents. If the reaction remains at Grade 1 or less, the infusion will resume at 50% of the previous rate after up to 60 minutes of interruption. Up-titration of the rate may be attempted according to Section 8.1.2, provided that the AE remains Grade ≤1. If more than 60 minutes of interruption are required, the AE will be treated as for a Grade 2 infusion-related reaction.

If the **infusion-related reaction is Grade** ≥2, interrupt the infusion and treat the reaction. For Grade 2 infusion reactions, if the AE improves to Grade 1 or less within 48 hours, retreatment will be reattempted on the next scheduled day without a dose escalation, following premedication with dexamethasone, montelukast, acetaminophen, diphenhydramine, and ranitidine, or similar agents. If tolerated well, dose escalation (if planned) may resume with the next dose. If the infusion-related reaction persists for >48 hours, it will be managed as for a Grade 3 infusion-related reaction.

For **Grade 3 or Grade 4 infusion-related reactions**, interrupt the infusion and treat the reaction. The next dose will be omitted. After the AE resolves, treatment will restart on the next subsequent scheduled dosing day with additional premedication. Dose reduction by 1 step must be applied (Table 4). Treatment will restart with the lead-in dose.

For CRS Grade 1, no dose modifications or delays are required.

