For CRS Grade 2 that resolves within 48 hours, the next dose should be given on schedule, but without a dose escalation. For CRS Grade 2 that persists for >48 hours or is present <48 hours before the next dose is scheduled, or a first episode of CRS Grade 3, the next dose will be omitted. After resolution of the AE, treatment will resume with the lead-in dose and a 1-step dose reduction. For CRS Grade 3 that fails to resolve to \(\leq\)Grade 1 within 72 hours, SAR440234 will be permanently discontinued. For a second or subsequent episode of CRS Grade 3, SAR440234 will be permanently discontinued. If CRS Grade >2 persists for >14 days after the last infusion, SAR440234 will be permanently discontinued.

For **CRS Grade 4**, the SAR440234 infusion must be stopped; no re-start is allowed. Treatment must be permanently discontinued.

Guidelines for the resumption of treatment and dose modification following treatment interruptions are provided in Table 5 (secondary to infusion-related reactions) and Table 6 (secondary to CRS).

Table 5 - Recommendations for resumption of treatment and dose modification following infusion-related reactions during SAR440234 infusion

Grade a	During SAR440234 Infusion (Infusion-related reaction)
1	Interrupt infusion and treat reaction, then resume the SAR440234 infusion at 50% of the rate previously achieved, and increase per Section 8.1.2, provided the event remains at Grade 1 or below. If AE requires interruption for >1 hour, treat as for Grade 2 event.
2	Interrupt infusion and treat reaction, then administer next dose on the next scheduled day without a dose escalation, but with additional premedication, provided AE has resolved within 48 hours. If tolerated well, dose escalation (if planned) may resume with subsequent doses.
	If AE persists for >48 hours, treat as for Grade 3 event.
3 or 4	Interrupt infusion and treat reaction. Omit next dose.
	After AE resolved, restart treatment on the next scheduled dosing day with additional premedication. Dose reduction by 1 step must be applied (Table 4). Treatment will restart with the lead-in dose.
	The reaction is a DLT if CRS occurs during Cycle 1.

a Grade of CRS according to the 2014 National Cancer Institute Consensus Guidelines (Appendix H) AE=adverse event, DLT=dose-limiting toxicity

Table 6 - Recommendations for resumption of treatment and dose modification following cytokine release syndrome after SAR440234 infusion is completed

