# 9 ASSESSMENT OF INVESTIGATIONAL MEDICINAL PRODUCT

#### 9.1 SAFETY

The major purpose of this Phase 1/2A study is to establish, based on DLTs, the MTD of SAR440234 administered IV weekly (except for Cycle 1 Week 1 in DL ≥3 when 2 administrations will be given) to patients with hematologic malignancy (R/R AML, B-ALL, or HR-MDS). Safety is thus the primary study endpoint and will be assessed continuously.

The safety profile will be assessed from the findings of physical examinations (preferably by the same physician in each center), laboratory tests, and reports of AEs, etc, and will be based on incidence, severity (as graded by the NCI-CTCAE v4.03; except for CRS, which will be graded according to the 2014 NCI Consensus Guidelines, Table 10), and cumulative nature of TEAEs (defined as AEs that develop or worsen in grade or become serious during the on-treatment period).

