# 13.4.4.2 Analyses of adverse events

Adverse events will be collected from the time informed consent is signed until at least 30 days after the last administration of the IMP, and will be categorized according to NCI-CTCAE v4.03, except for CRS, which will be graded according to the 2014 NCI Consensus Guidelines (Table 10). All AEs will be classified by system organ class and preferred term according to the latest available version of the MedDRA dictionary.

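### The grading scale and DLT status of infusion-related reactions are not stated consistently across Sections 6.2.1, 6.5.3 (Table 5), 9.1, 9.1.1 and 13.4.4.2, so the same reaction can be handled differently by section

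*Protocol*

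**What the plan says.** Protocol Section 6.5.3 separates two events by timing. "CRS-like symptoms or signs that occur during infusion will be referred to as infusion-related reactions", while signs that "develop or persist after the infusion ends will be referred to as CRS". It then puts both on one scale: "Infusion-related reactions and CRS will be graded according to the 2014 NCI Consensus Guidelines (Appendix H").

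The general rule for adverse events is different. The Clinical Trial Summary (Dose Escalation Part) applies CTCAE v4.03 "except for cytokine release syndrome (CRS), which will be graded according to the 2014 NCI Consensus Guidelines". Section 9.1 has severity "as graded by the NCI-CTCAE v4.03; except for CRS, which will be graded according to the 2014 NCI Consensus Guidelines, Table 10". Section 13.4.4.2 uses CTCAE v4.03 "except for CRS, which will be graded according to the 2014 NCI Consensus Guidelines (Table 10"). Sections 9.1.1 and 9.1.2 are looser: they give CTCAE or, for grading CRS, the Consensus Guidelines in Table 10, whichever is appropriate.

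The DLT lists in Sections 6.2.1 and 9.1.1 name Grade 3 or 4 CRS, and prolonged or late Grade 2 CRS. They do not name infusion-related reactions. The graded criterion that could cover one is "Any Grade ≥3 nonhematological AE, unless either caused by disease progression or an obviously unrelated cause", which goes on to exempt laboratory abnormalities that have no clinical consequences and resolve within 5 days.

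Table 5, on reactions during the infusion, says in its Grade 3 or 4 row: "The reaction is a DLT if CRS occurs during Cycle 1". Table 6, on CRS after the infusion, uses the same sentence.

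**The concern.** An infusion-related reaction is an adverse event and, by Section 6.5.3's own label, is not CRS. The CRS exception therefore does not reach it, and the general rule would put it on CTCAE, while Section 6.5.3 puts it on the 2014 scale. The dose action would follow one scale, and the DLT call and adverse event tables could follow another.

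Acute reactions are a central expected toxicity of this T-cell engager. Their incidence, pooled with CRS, is a primary Dose Escalation endpoint. Under Section 6.2.2 and Table 3, one DLT in six patients allows escalation and two define the MAD, so a single reaction classed differently can change the decision at a dose level.

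**Working it through.** There is no plan figure to reproduce. The check sets the texts side by side and then illustrates what is at stake.

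**Step 1: scale.**

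| Place | Scale for CRS | Scale for infusion-related reactions |
|---|---|---|
| 6.5.3, Table 5 | 2014 scale, Appendix H | 2014 scale, Appendix H |
| Summary, 9.1, 13.4.4.2 | 2014 scale (Table 10 in 9.1 and 13.4.4.2) | Not named; falls to CTCAE v4.03 because only CRS is excepted |
| 9.1.1, 9.1.2 | 2014 scale, Table 10 | Not named; CTCAE or the 2014 scale as appropriate |
| SAP 4.7.2 | Not stated | Not stated; SAP Table 6 has rows for DLT and CRS but none for these reactions |

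The 2014 scale itself appears in two versions. The Grade 3 oxygen criterion is below 40% in Table 10 and above 40% in Appendix H.

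**Step 2: route to a DLT (6.2.1).** Grade 3 or 4 CRS is a DLT with no laboratory exemption. A Grade 3 or higher nonhematological event is a DLT unless, among other exceptions, it is a laboratory abnormality without clinical consequences that resolves within 5 days. Both Table 10 and Appendix H place a Grade 4 transaminase rise at CRS Grade 3. A finding of that kind could therefore be a DLT by the CRS route and exempt by the general route. This difference exists on paper; the affected group is probably narrow.

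**Step 3: Table 5.** Take a Grade 3 reaction in Cycle 1 that resolves before the infusion ends, so that it never becomes CRS under 6.5.3.
- Under 6.2.1 it is a DLT unless one of the stated exemptions applies. No CRS is required.
- Under Table 5 read as a timing limit, it is a DLT, and the two sections agree.
- Under Table 5 read literally with the 6.5.3 labels, CRS has not occurred, so the sentence does not make it a DLT, and the sections disagree.

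The labels do not settle which reading is meant. The Table 5 footnote calls its grades grades of CRS, and the Grade 4 CRS paragraph of 6.5.3 requires the infusion to be stopped, which applies the CRS label to an event during infusion.

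**Step 4: illustration.** Under Table 3 a level is cleared with 0 DLTs in 3 patients, or with 1 in 3 followed by 0 in the next 3. With per-patient DLT probability t:

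P(clear) = (1−t)³ + 3t(1−t)² × (1−t)³

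Let q be the rate of other DLTs and r the rate of reactions that are DLTs under one reading only. Both are assumed, and the events are taken as independent. Not counted: t = q. Counted: t = 1 − (1−q)(1−r).

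With q = 10% and none counted: 0.9³ + 3(0.1)(0.9)⁵ = 0.729 + 0.177 = 0.906.

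| r (q = 10%) | t | P(clear) | Fall from 0.906 |
|---|---|---|---|
| 1% | 0.109 | 0.891 | 0.015 |
| 2% | 0.118 | 0.875 | 0.031 |
| 5% | 0.145 | 0.824 | 0.082 |
| 10% | 0.190 | 0.730 | 0.176 |

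With q = 20%, P(clear) is 0.709 if none are counted, 0.622 at r = 5% and 0.536 at r = 10%.

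**The case against.** The strongest reply is that Table 5 and 6.2.1 agree when read sensibly. The Table 5 sentence recurs in Table 6, where CRS is already present and the clause can only restrict timing to Cycle 1. A reader might infer that Table 5 makes a reaction a DLT only when CRS follows. The text does not say that, and the timing reading is at least as natural. This stands. What remains is that the sentence allows two readings.

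Second, few reactions are affected. At Grade 3 or 4 the infusion is interrupted and treatment restarts on a later dosing day. If interruption counts as the end of the infusion, signs that persist beyond it become CRS, and Grade 3 or 4 CRS is a DLT. Likewise, a Grade 2 reaction lasting more than 48 hours outlasts an infusion of 1 to 19 hours and falls under the CRS rule. This largely stands and argues for a small r. However, 6.5.3 speaks of the infusion ending and the title of Table 6 of its completion, and neither says how an interrupted infusion counts.

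Third, a reader might infer that CTCAE is prescribed for these reactions throughout, or that one reaction is shown to receive two grades. Neither is supported. No section assigns CTCAE to them by name, Sections 9.1.1 and 9.1.2 leave room for the 2014 scale, and the CTCAE criteria are not in the documents.

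Fourth, there are safeguards. Potential DLTs go to the Study Committee, the DLT list has a judgement-based catch-all, the SAP takes DLTs from the eCRF DLT page, and the primary endpoint pools CRS with acute infusion reactions, so its incidence does not depend on the label. These soften the consequence. But the committee's stated task in 9.1.1 is relationship to the drug, not the choice of scale, and the grade-based tables are not protected by pooling.

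**Conclusion.** The point holds as an inconsistency to reconcile. Section 6.5.3 and the general adverse event rule lead to different scales for an infusion-related reaction, the DLT lists do not name it, and Table 5 can be read in two ways. For a reaction that resolves before the infusion ends, grade and DLT status can differ by section. The documents do not show that they will, or how often.

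The probabilities above are illustrations that rest on independence and on assumed q and r. A reader might take the fall of about 18 percentage points at r = 10% as an estimate. No figure in the documents supports that rate, and at r = 1% the fall is about 1.5 points.

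The SAP records early termination, which limits the effect on further escalation. It keeps the primary safety analyses (Sections 4.3 and 4.7), so the reporting question remains. Because the rule feeds the 3+3 decision and a primary safety endpoint, and clarifying it is cheap, it should be corrected.

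**What to change.** - Reconcile the Clinical Trial Summary and Sections 6.2.1, 6.5.3 (with Table 5), 9.1, 9.1.1, 9.1.2 and 13.4.4.2, so that one stated scale governs infusion-related reactions for dose action, DLT assessment and adverse event tables.
- State the DLT status of these reactions once, in the DLT list, and have Table 5 refer to it. Say whether an interrupted infusion counts as ended when separating them from CRS.
- Reconcile Table 10 with Appendix H, including the Grade 3 oxygen criterion, so that every section cites the same version of the 2014 scale. Without this, naming one scale would still leave two versions in force.
- Add a line to the SAP giving the scale used for infusion-related reactions and where they appear in the AESI and adverse event outputs.

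Which scale and which DLT rule apply is for the sponsor to decide. The cost is protocol wording and one SAP line; no new data are needed, because the signs are already recorded.

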Grade a	After SAR440234	Infusion completed			
	Duration of event <48 hours and event resolved >48 hours before next dose is due	Duration of event >48 hours and/or persistent <48 hours before next dose is due			
1	Administer the next dose when planned and escalate the dose (if planned).				
2	Administer the next dose when planned, but do	Omit next dose.			
	not escalate next dose. If tolerated well, dose escalation may resume subsequently.	After AE resolved, restart treatment. Dose reduction by 1 step must be applied (Table 4). Treatment will restart with the lead-in dose.			
		The reaction is a DLT if CRS occurs during Cycle 1.			
		If CRS Grade >2 persists for >14 days after the last infusion, SAR440234 will be permanently discontinued.			
3	Omit ne	ext dose.			
	After AE resolved, restart treatment. Dose reduction by 1 step must be applied (Table 4). Treatment w restart with the lead-in dose. Do not escalate past the target dose.				
	The reaction is a DLT if CRS occurs during Cycle 1				
		or if it recurs again, treatment will be permanently ntinued			
4	Permanent d	iscontinuation.			

a Grade of CRS according to the 2014 National Cancer Institute Consensus Guidelines (Appendix H) AE=adverse event, CRS=cytokine release syndrome, DLT=dose-limiting toxicity

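### One sentence in Protocol Section 6.5.3 allows the next dose after short Grade 2 CRS without the 48-hours-before-dose condition that the following sentence, Table 6 and the DLT definition apply

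*Protocol*

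**What the plan says.** Protocol Section 6.5.3 handles Grade 2 CRS in two consecutive sentences. The first reads: "For CRS Grade 2 that resolves within 48 hours, the next dose should be given on schedule, but without a dose escalation". The second covers events that last longer than 48 hours and also any event that "is present <48 hours before the next dose is scheduled, or a first episode of CRS Grade 3, the next dose will be omitted". After an omitted dose, treatment resumes with lead-in dosing and a one-step reduction.

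Table 6 in the same section states both branches. Its column for giving the next dose requires two things together: "Duration of event <48 hours and event resolved >48 hours before next dose is due". Its other column applies when either condition fails. For Grade 2 it omits the dose and labels the event a DLT if it occurs in Cycle 1.

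The DLT definition in Section 6.2.1 uses the same either/or test: "Grade 2 CRS if it persists for >48 hours or is present <48 hours before the time" that the next planned dose falls due. The Clinical Trial Summary and Section 9.1.1 repeat it.

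**The concern.** Of these statements, only the first sentence of the pair leaves out proximity to the next dose. A Grade 2 event can be short enough to meet that sentence and still be present inside the last 48 hours before the next infusion. For such an event one instruction gives the dose on schedule. The other omits it, then restarts lower with lead-in dosing.

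Section 4.6 names severe CRS as an anticipated risk, and the two instructions collide most easily at the shortest dosing interval in the protocol. What is at stake is whether a patient who has just had Grade 2 CRS is dosed again three days after the first infusion.

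**Working it through.** The documents state no figure to reproduce. The check asks when both instructions apply to the same event.

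**Inputs**
- Cycle 1 dosing days at dose level 3 and above are 1, 4, 8 and weekly thereafter (Section 6.2.1). Nominal gaps between infusion starts are 72 h, 96 h and 168 h. Section 1.3.1 confirms the 72 h, with a 72-hour sample drawn just before the next infusion.
- Infusions last 1 to 19 hours (Section 1.2.1, footnote on hospitalization).
- The documents give no CRS onset times for this drug. Onsets of 2, 6 and 19 h after the start of infusion are assumptions; 19 h is the end of the longest planned infusion. Section 6.5.3 reserves the term CRS for signs after the infusion ends, so the 2 h and 6 h cases presuppose an infusion that has ended by then.

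**Conditions**, with gap G, onset t and duration d in hours:
- The first sentence gives the dose if d ≤ 48.
- The second sentence and Table 6 omit the dose if the event is still present after hour G − 48, that is, if t + d > G − 48.
- Both apply if G − 48 − t < d ≤ 48.

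**Results**

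| Gap | Cut-off hour (G − 48) | Onset 2 h | Onset 6 h | Onset 19 h |
|---|---|---|---|---|
| Day 1 to Day 4, 72 h | 24 | 22 < d ≤ 48 | 18 < d ≤ 48 | 5 < d ≤ 48 |
| Day 4 to Day 8, 96 h | 48 | 46 < d ≤ 48 | 42 < d ≤ 48 | 29 < d ≤ 48 |
| Weekly, 168 h | 120 | none | none | none |

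On the weekly gap an overlap needs 120 − t < 48, so onset must be later than hour 72. In the 72 h gap, an event that starts after hour 24 meets both instructions at any duration up to 48 h, provided it resolves before Day 4.

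**After the correction.** If the first sentence also requires resolution more than 48 hours before the next dose, it needs t + d < G − 48. The second sentence needs t + d > G − 48. No event meets both, and every overlapping case goes to omission.

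**The case against.** The strongest reply is that the two sentences are adjacent and the second names the specific case, so it can be read as an exception to the first. Table 6 and all three statements of the DLT definition agree with it, and Sections 6.5.3 and 6.7.1 send sites to Tables 5 and 6 for resuming treatment. This largely stands: the intended rule can be recovered. It does not make the first sentence right. Nothing in the second marks it as an exception, and Section 6.5 describes the tables as summaries of the text and does not say that they override it.

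The consequence is also contained. Patients at dose level 3 and above stay in hospital from Day 1 until 72 hours after the third infusion. Grade 2 CRS requires transfer to intensive care (Table 11), potential DLTs are reported to the sponsor within 24 hours (Section 9.1.1), and dexamethasone is repeated at later infusions (Section 6.7.1). Even on the mistaken reading the event has resolved to Grade 1 or less and the dose is not escalated.

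A reader might infer a parallel gap for Grade 2 infusion-related reactions. For these, Section 6.5.3 says that "if the AE improves to Grade 1 or less within 48 hours, retreatment will be reattempted on the next scheduled day", and Table 5 gives the next dose "without a dose escalation, but with additional premedication, provided AE has resolved within 48 hours", again with no proximity condition. The title of Table 6, "following cytokine release syndrome after SAR440234 infusion is completed", might also seem to leave out an infusion that was stopped early. The documents do not support this. Section 6.5.3 says that "CRS-symptoms or signs that develop or persist after the infusion ends will be referred to as CRS", and it refers CRS to Table 6, so a reaction that outlasts the infusion follows Table 6. A Day 1 reaction confined to an infusion of at most 19 h is over at least 72 − 19 = 53 h before Day 4, outside the 48-hour window.

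**Conclusion.** The sentence is wrong as written, and the point is minor. It is an internal inconsistency in a safety dosing rule, and the correct rule stands beside it and in Table 6.

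The ranges above are windows in which the instructions disagree. They rest on nominal dosing days and assumed onsets, and no frequency can be drawn from them.

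Two stronger readings do not hold. A reader might infer that DLT counts or cohort decisions are compromised. They are not: the DLT definition contains the proximity test in all three places and does not depend on the faulty sentence. A reader might also infer that the problem exists only at dose level 3 and above. It is widest there, because of the Day 4 infusion, but late-onset CRS on the weekly schedule can meet both instructions at any dose level.

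**What to change.** In the quoted sentence of Section 6.5.3, after the reference to resolving within 48 hours, insert: *and has resolved >48 hours before the next dose is due*. The rest of the sentence stays, including the bar on escalation.

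The cost is one wording edit. Table 5, Table 6, the DLT definition, data collection and the analyses do not change. The SAP (Sections 4.3 and 4.9) records early termination of the trial, so the benefit lies in the protocol as a correct document and in any later protocol that reuses this dosing text.

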#### 6.5.2 Dose modifications

When more than 1 AE is present, treatment modifications will be in accordance with the guidelines for the most severe AE.

Dose modifications, if required, will be a reduction of 1 step (Table 4) from the last administered dose. For example, if the last administered dose was (Step 5), a 1 step dose reduction would be to (Step 4). Otherwise, the lead-in dose will be based on the last administered dose.

Step Target Dose (ng/kg)

Lead-in Dosing When Restarting Treatment (if Applicable)

[figure not shown]
1
2
3
4
5
6
7
8
9
10

Table 4 - Definition of dose steps

IV=intravenous

11

The target dose is the dose that will be given every 7 days after lead-in dosing. When there is a dose delay of 2 days (ie, <10 days from the last infusion), the dose may be given without the lead-in dose.

If an AE requiring dose reduction and lead-in dosing occurs following the dose, the 1 ng/kg weekly dose will be administered.

If an AE requiring dose reduction occurs following the dose, the IMP will be discontinued.

After a safe and effective dose has been defined, individual patients who are still on study treatment at a different dose may be considered for treatment at another dose or schedule from which they were originally assigned, if this dose and schedule is thought to be safer and/or more effective, and the Sponsor and Investigator agree that it would be beneficial for the patient. If the dose exceeds the originally assigned dose, lead-in dosing will be administered.

Property of the Sanofi Group - strictly confidential

Page 59

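### Protocol 6.5.3 directs restart after a resolved Grade 4 infusion-related reaction, although Grade 4 CRS on the same scale ends treatment; Grade 3 infusion-related reactions also have no second-episode stop

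*Protocol*

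**What the plan says.** Section 6.5.3 grades both kinds of reaction by the 2014 NCI Consensus Guidelines. Timing alone separates them. The first label covers the infusion itself: "CRS-like symptoms or signs that occur during infusion will be referred to as infusion-related reactions". The second takes over once the infusion has finished: "CRS-symptoms or signs that develop or persist after the infusion ends will be referred to as CRS". Table 10 defines Grade 4 as life-threatening symptoms, a need for ventilator support, or Grade 4 organ toxicity other than transaminitis.

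The instructions then diverge.

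- **Grade 3 or 4 infusion-related reaction (text and Table 5).** Interrupt, treat and omit the next dose. "After the AE resolves, treatment will restart on the next subsequent scheduled dosing day with additional premedication". The restart is one dose step lower and begins with lead-in dosing.
- **Grade 4 CRS (text and Table 6).** "the SAR440234 infusion must be stopped; no re-start is allowed. Treatment must be permanently discontinued".
- **Grade 3 CRS.** A first episode allows a reduced restart, but failure to fall to Grade 1 or less within 72 hours ends treatment. So does recurrence: "For a second or subsequent episode of CRS Grade 3, SAR440234 will be permanently discontinued". Neither stop appears for Grade 3 infusion-related reactions.

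Section 6.7.1 sends sites to Tables 5 and 6 to decide whether and when a patient may resume.

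**The concern.** Two patients can have the same life-threatening grade on the same scale and receive opposite instructions because of when the signs appeared. The Grade 4 CRS sentence itself tells staff to stop the infusion, which makes sense only while one is running. A Grade 4 event during an infusion can therefore be read under either rule.

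This setting is foreseeable. Section 4.5.4 says that CRS with therapeutic antibodies typically starts within minutes to hours of the start of infusion, infusions here last 1 to 19 hours, and Section 8.1.2 expects infusion-related reactions. At stake is mandatory-sounding rechallenge after a life-threatening reaction, and unlimited repeat episodes at Grade 3 subject only to successive dose reductions.

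**Working it through.** **Step 1: compare the rules.**

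| Event | Infusion-related reaction | CRS |
|---|---|---|
| Grade 4, resolved | Restart one step lower | Permanent stop |
| Grade 3, first episode | Restart one step lower | Restart one step lower |
| Grade 3, not resolved within 72 hours | No stop stated | Permanent stop |
| Grade 3, second episode | No stop stated | Permanent stop |

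**Step 2: find the boundary.** Signs that persist after the infusion ends become CRS, so a persisting Grade 4 reaction should reach the CRS stop. Two provisions blur this for an interrupted infusion. Table 6 is titled for "cytokine release syndrome after SAR440234 infusion is completed", and an interrupted infusion is not completed. For a Grade 2 reaction, "If the infusion-related reaction persists for >48 hours, it will be managed as for a Grade 3 infusion-related reaction", so a reaction lasting beyond the infusion can keep its label. The clear gap is a Grade 4 reaction that resolves once the infusion is stopped.

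**Step 3: look for another rule that closes the gap.**

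- Section 6.5.5 and Table 9 hold the general second-episode stops but exclude CRS and infusion-related reactions. For other nonhematological Grade 4 events, restart needs resolution within 14 days, perceived benefit, and Investigator and Sponsor agreement. Table 5 has none of these conditions.
- Section 6.5.2 has a stop tied to a single dose, whose value is not shown: "If an AE requiring dose reduction occurs following the dose, the IMP will be discontinued".
- Section 6.7.5 bars Cycle 2 after a DLT, but only in Dose Escalation, and it does not block restart within Cycle 1.
- Section 11.1.1 says treatment should stop when the Investigator judges continuation detrimental, including for an unacceptable adverse event. This depends on judgment.

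None of these requires a stop for a resolved Grade 4 infusion-related reaction in general.

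**Step 4: count the infusions still scheduled.** The dosing days come from Sections 4.5.3 and 12.5. Cycle 1 at dose level 3 or above uses Days 1, 4, 8, 15, 22, 29 and 36. Dose levels 1 and 2 use the same days without Day 4, and later cycles use Days 1, 8, 15, 22, 29 and 36. Rule: after a reaction at infusion *i*, omit *i*+1 and restart at *i*+2. With *n* infusions in the cycle, *n* − *i* − 1 remain (zero at the last infusion).

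| Reaction day | Level ≥3 (*n* = 7): left in Cycle 1 | Days to restart | Levels 1–2 (*n* = 6): left in Cycle 1 | Days to restart |
|---|---|---|---|---|
| 1 | 7−1−1 = 5 | 8−1 = 7 | 6−1−1 = 4 | 15−1 = 14 |
| 4 | 7−2−1 = 4 | 15−4 = 11 | – | – |
| 8 | 7−3−1 = 3 | 14 | 6−2−1 = 3 | 14 |
| 15 | 7−4−1 = 2 | 14 | 6−3−1 = 2 | 14 |
| 22 | 7−5−1 = 1 | 14 | 6−4−1 = 1 | 14 |
| 29 or 36 | 0 | – | 0 | – |

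Only on Days 29 and 36 does the Dose Escalation bar on Cycle 2 act as a full stop. In the Expansion Part, a Day 1 reaction leaves up to 7 + 6 − 2 = 11 infusions over two cycles on the level ≥3 schedule, or 6 + 6 − 2 = 10 on the level 1–2 schedule.

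**The case against.** The Grade 4 gap is narrow. Recovery means Grade 1 or less, and a patient on a ventilator or with Grade 4 organ toxicity will rarely recover as the infusion stops. On an ordinary reading, a stopped infusion has ended, so most real Grade 4 events become CRS and reach the stop. The CRS sentence can also be read as covering events during infusion. This narrows the scope, but the protective reading contradicts the explicit Grade 3 or Grade 4 restart instruction and Table 5, so the conflict remains.

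The infusion counts do not measure risk. Some of the remaining infusions would be lead-in doses, and the restart lead-in schedule in Table 4 is not shown. The largest counts use Day 1, a lead-in dose where the Section 6.5.2 stop may be most likely to apply. These limits stand: the counts show only how much scheduled exposure the restart rule leaves open.

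Rechallenge after Grade 4 is also accepted elsewhere, in Section 6.5.5, and copying those conditions into Table 5 would be a smaller change. That is fair, but it would still treat Grade 4 on this scale differently from Grade 4 CRS, and the protocol gives no reason for that difference. Pooling Grade 3 episodes across the two labels is more debatable, because it goes beyond aligning existing rules.

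**Conclusion.** The inconsistency holds as written and should be fixed. A Grade 4 infusion-related reaction that resolves once the infusion stops leads to restart, while Grade 4 CRS ends treatment. Grade 3 infusion-related reactions lack the second-episode stop that applies to Grade 3 CRS. The safeguards elsewhere reduce the risk but do not mandate a stop for these events.

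In Dose Escalation, 1 to 5 Cycle 1 infusions remain at level 3 or above after a reaction on Days 1 to 22, and 1 to 4 at levels 1 and 2. This assumes resolution before the restart day, one infusion on each remaining scheduled day, and no trigger of the Section 6.5.2 stop. No frequency can be given. Sample size, alpha and power are unaffected, and DLT counting essentially so. SAP Section 4.3 reports early termination, so the Expansion figures describe the plan as written.

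**What to change.** 1. In Section 6.5.3 and Table 5, separate Grade 4 from Grade 3 and require permanent discontinuation for any Grade 4 reaction on this scale, whatever its timing. This is the essential change. It also fits the rationale recorded for Amendment 01 in Appendix K, which treats Grade 4 CRS at any time point as ending treatment (cited only as context for intent).
2. Add a permanent stop at the second Grade 3 episode. Counting infusion-related and CRS episodes together is preferable, because one scale covers both. If pooling is not accepted, give infusion-related reactions their own second-episode stop.
3. State that an interrupted infusion that is not resumed counts as ended, so that persisting reactions follow the CRS rules, including the 72-hour stop.

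The cost is protocol wording, plus the loss of rechallenge for a few patients with a brief Grade 4 or repeat Grade 3 reaction during infusion.
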